6.3.2 Hematologic Toxicity

- CBC will be obtained on days 1 and 15 of each cycle.
- Patient must have ANC > 1000 and platelets > 75,000 in order to treat on any given treatment day.

C1D1 dosing AND subsequent Day 1 and Day 15 dosing if previous dose was given:

ANC Platelets		%Previous dose 5-	%Previous dose		
		FU/LV	Oxaliplatin		
>1000 and	>75,000	100	100		

≤1000	≤75,000	HOLD dose and	HOLD dose and
		reassess in 2 weeks	reassess in 2 weeks
≤500	≤50,000	HOLD dose and	HOLD dose and
		reassess in 2 weeks	reassess in 2 weeks

Day 1 and 15 dosing if the immediate previous Day 1 or 15 dose was HELD:

ANC	Platelets	%Previous dose 5- FU/LV	%Previous dose Oxali
>1000 and	>75,000	75% of previous dose if either ANC was 501-1000 or Plts were 51,000- 75,000 50% of previous dose if either ANC was ≤500 or Plts	75% of previous dose if either ANC was 501-1000 or Plts were 51,000- 75,000 50% of previous dose if either ANC was ≤500 or Plts
<1000 or	<75.000		
≥1000 or	≥75,000	reassess in 2 weeks	reassess in 2 weeks
≤500 or	≤50,000	HOLD dose and reassess in 2 weeks	HOLD dose and reassess in 2 weeks

If the patient requires two consecutive doses of FOLFOX to be held for hematologic toxicity, the patient should get 50% of the previous dose of FOLFOX if they meet criteria for treatment on the next scheduled treatment day.

In addition, at any time during a cycle, if the patient experienced 1) febrile neutropenia or 2) any Grade 3 or higher hematologic toxicity (excluding thrombocytopenia and neutropenia, which will be addressed using the tables above) while on FOLFOX, then 5-FU and Oxaliplatin should be held until the toxicity resolves to <Grade 2. When the patient meets treatment criteria, the 5-FU and Oxaliplatin should be resumed at 75% of most recent dose for all subsequent doses.

Doses of chemotherapy that have been reduced will not be re-escalated. A maximum of 4 dose reductions are allowed for 5-FU and Oxaliplatin (with the minimum allowed dose of 5-FU being 380 mg/m2/day and the minimum allowed dose for oxaliplatin being 27 mg/m2).

No held doses will be made up. If a patient misses a dose for toxicity, the patient will proceed to the next treatment day or cycle as scheduled.

If the FOLFOX is held for > 6 weeks (i.e. three consecutive doses of FOLFOX are held), FOLFOX will be permanently discontinued, and the patient can remain on the study as long as they are receiving Sorafenib.

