6.4.1 Dose Reduction Levels

The starting dose of sorafenib is 400 mg twice a day. Study medication will be administered daily on a continuous basis.

Doses will be delayed or reduced for clinically significant hematologic and nonhematologic toxicities that are related to protocol therapy according to the guidelines shown in the Dose Delays/Dose Modifications table that follows. Dose modifications will follow predefined dose levels: Dose adjustments for hematologic toxicity are based on the blood counts obtained in preparation for the day of treatment.

Dose modification levels for sorafenib							
Dose	Sorafenib						
Starting Dose	400 mg twice daily						
1 st Dose Reduction Level	400 mg once daily						
2 nd Dose Reduction Level	200 mg once daily						

Recommended Dose Modification of sorafenib for Hematologic Toxicities										
Toxicity	ANC(x 10 ⁹ /L)	Hemoglobin (g/dL)	Platelets (x 10 ⁹ /L)	Sorafenib						
Grade 1	<lln-1.5< td="">< LLN – 10.0	<lln-75< td="">Treat on time No change	</lln-75<>	</lln-1.5<>	< LLN – 10.0	<lln-75< td="">Treat on time No change	</lln-75<>	Treat on time No change						
Grade 2	≥ 1.0 to < 1.5	< 10.0 - 8.0	≥ 50 to < 75	Treat on time No change						
Grade 3	≥ 0.5 to < 1.0	< 8.0 - 6.5	≥ 25 to < 50	Treat on time Reduce by one dose level						
Grade 4	< 0.5	Life-threatening consequence; urgent intervention indicated	<25	Delay sorafenib until toxicity resolves to Grade 2 or less then Reduce by two dose levels ¹						
Febrile Neutropenia				Sorafenib held until toxicity has resolved to Grade 2 or less; when sorafenib is restarted, reduce by one dose level ²						

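### When febrile neutropenia coincides with a treatment-day ANC below 500, the dose rules for FOLFOX and for sorafenib conflict and no rule says which governs

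*Combined protocol and SAP*

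**What the plan says.** **FOLFOX (section 6.3.2).** One table applies to "Day 1 and 15 dosing if the immediate previous Day 1 or 15 dose was HELD". In it, once counts permit treatment, 5-FU/LV and oxaliplatin restart at 75% if the ANC behind the hold was 501 to 1000, and at "50% of previous dose if either ANC was ≤500 or Plts" fell to the corresponding low range. A sentence after the table gives 50% of the previous dose when two consecutive FOLFOX doses are held for hematologic toxicity. A further paragraph, introduced as an addition to these rules, applies "at any time during a cycle, if the patient experienced 1) febrile neutropenia or 2) any Grade 3 or higher hematologic toxicity". Its second item carries the parenthesis "excluding thrombocytopenia and neutropenia, which will be addressed using the tables above". For both items it holds 5-FU and oxaliplatin, and then "the 5-FU and Oxaliplatin should be resumed at 75% of most recent dose for all subsequent doses".

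**Sorafenib (sections 6.4.1 and 6.4.2).** The Grade 4 row (ANC below 0.5 x 10^9/L) reads "Delay sorafenib until toxicity resolves to Grade 2 or less then Reduce by two dose levels". The febrile-neutropenia row, directly beneath it, holds the drug to the same recovery threshold, and "when sorafenib is restarted, reduce by one dose level". Under the footnotes in 6.4.2, the Grade 4 row means discontinuation for a patient already on 400 mg or 200 mg once daily. The febrile row means discontinuation only for a patient already on 200 mg once daily.

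**Permanence.** Section 6.3.2 bars re-escalation of chemotherapy. The text closing section 6.4 bars it for sorafenib.

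**The concern.** A patient who is febrile and neutropenic, and whose Day 15 ANC is, for example, 400, satisfies two FOLFOX rules and two adjacent rows of the sorafenib table. The rules give different doses. For sorafenib they cannot both be followed, and for a patient on 400 mg once daily one row stops the drug while the other continues it. Because reductions are permanent, one reading of the text on one day fixes the patient's later exposure to all three drugs. Two clinicians following the protocol in good faith could treat the same event differently. That bears on patient safety and on how the tolerability data, a secondary objective, should be read.

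**Working it through.** **1. Reproduce the section's own figures.** Section 6.3.2 allows at most four reductions, with floors of 380 mg/m2/day for 5-FU and 27 mg/m2 for oxaliplatin. Four successive 25% cuts multiply the starting dose by 0.75^4 = 0.3164.
- 5-FU: 1200 x 0.3164 = 379.7, stated as 380.
- Oxaliplatin: 85 x 0.3164 = 26.9, stated as 27.

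Both agree, so the percentages are read as multipliers of the last dose given.

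**2. Does the parenthesis settle the overlap?** No. Febrile neutropenia is item 1. The exclusion of neutropenia and thrombocytopenia is attached to item 2, the other hematologic toxicities of Grade 3 or higher. It sends plain neutropenia to the tables and says nothing about a patient who meets item 1 and the table together.

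**3. Put the two rules side by side** for a febrile patient whose dose was held on a treatment-day ANC below 500:

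| Dose before the event | Febrile-neutropenia rule | ANC rule | If both FOLFOX cuts apply (0.75 x 0.50 = 0.375) |
|---|---|---|---|
| 5-FU 1200 mg/m2/day | 900 | 600 | 450 |
| 5-FU 2400 mg/m2 per treatment | 1800 | 1200 | 900 |
| Oxaliplatin 85 mg/m2 | 63.75 | 42.5 | 31.9 |
| Sorafenib 400 mg bid | 400 mg once daily | 200 mg once daily | – |
| Sorafenib 400 mg once daily | 200 mg once daily | discontinue | – |
| Sorafenib 200 mg once daily | discontinue | discontinue | – |

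**4. What the choice leaves in reserve.** Count the further 25% cuts possible before a FOLFOX floor is breached, allowing for the rounding of the floors.
- From 75%: 900 → 675 → 506 → 380, three cuts.
- From 50%: 600 → 450, one cut; the next gives 337.5, below 380.
- From 37.5%: none, since 450 x 0.75 = 337.5.

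Oxaliplatin gives the same counts: 63.75 → 47.8 → 35.9 → 26.9; 42.5 → 31.9, then 23.9; and 31.9, then 23.9.

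**5. A second collision in 6.3.2.** If febrile neutropenia causes two consecutive FOLFOX doses to be held, the consecutive-hold sentence gives 50% and the febrile paragraph gives 75%, whatever the ANC.

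**6. Where the rules do not collide.**
- The 50% table rule needs a dose held on a Day 1 or Day 15 count. An afebrile mid-cycle ANC of 400 that recovers above 1000 by the treatment day gets 100%, provided the previous dose was given and platelets also qualify.
- For a hold at ANC 501 to 1000, the table and the febrile paragraph both name 75%.
- The sorafenib Grade 4 row needs an ANC strictly below 0.5. At exactly 500 the count is Grade 3, a one-level reduction, which is the same size as the febrile row.
- At sorafenib 200 mg once daily both rows end in discontinuation.

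**The case against.** The strongest reply is that the overlap is narrow and the text can be read sensibly. The febrile paragraph is framed as supplementing the tables, so a reader could keep the 50% rule in force whenever the table is met. The sorafenib table is also headed as recommended modifications. The first argument shows that one reading is available, but not that the protocol chooses it: a supplement could equally multiply the cuts or govern alone. The second helps little, because section 6.4.1 says modifications follow predefined levels, and the footnotes state discontinuation outright.

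The reply is right about scale. A reader might infer that the protocol systematically treats febrile neutropenia more leniently than afebrile severe neutropenia for all three drugs, so that adding fever lessens the reduction. The documents do not support that:
- For a mid-cycle nadir that recovers, the febrile rule is the stricter one (75% against 100%).
- At an ANC of exactly 500 the sorafenib reductions are equal.
- Fever lessens a cut only if the febrile rule displaces the ANC rule, which the text does not say.
- The documents neither define febrile neutropenia by ANC nor rank it against afebrile Grade 4 neutropenia.

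A reader might also take the 6% febrile-neutropenia rate in section 6.2 and arrive at 0.06 x 40 = 2.4 affected patients. That rate comes from a second-line colorectal cancer trial of oxaliplatin with 5-FU/LV. It also counts all febrile neutropenia, not the subset with a held dose and a treatment-day ANC below 500. The 63% neutropenia reported in section 2.4 for the sorafenib, capecitabine and oxaliplatin regimen says nothing about febrile events or the overlap.

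**Conclusion.** The point stands in limited form. For a patient with febrile neutropenia and a treatment-day ANC below 500, the protocol states two different FOLFOX restart doses and two different sorafenib reductions, with no rule of precedence and no statement on whether cuts combine. This is a conflict between written rules rather than a missing detail.

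For one patient at full dose, the chemotherapy restart spans 37.5% to 75% of the starting dose, and sorafenib differs by a factor of two. For a patient on sorafenib 400 mg once daily, the difference is between stopping and continuing. The 37.5% figure assumes the cuts multiply, which the text leaves open. The FOLFOX table conflict requires a held Day 1 or Day 15 dose, and the sorafenib conflict requires an ANC strictly below 0.5 x 10^9/L. The separate conflict with the consecutive-hold rule requires that febrile neutropenia caused both holds.

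The number of patients affected is some subset of febrile-neutropenia cases and cannot be estimated from the documents. No effect on the TTP analysis is claimed.

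**What to change.** Reconcile three places in section 6.3.2 with one another: the held-dose table, the consecutive-hold sentence and the febrile-neutropenia paragraph. Reconcile the Grade 4 and febrile-neutropenia rows in section 6.4.1 together with their footnotes in 6.4.2. For each drug, state which rule governs when both are met, and whether reductions from a single event combine. The choice of dose and the ordering of reductions belong to the investigators, and none is proposed here.

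The cost is one amendment to two tables and their accompanying text, with no added procedures or data collection. If patients have already met the overlap, record which rule was applied so that exposure and tolerability can be reported accurately.

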6.3.3 Non-Hematologic Toxicity

6.3.3.1 Diarrhea

Anti-diarrheal agents should be prescribed for diarrhea. If greater than or equal to Grade 3 uncontrolled diarrhea despite maximal antidiarrheal therapy, temporarily discontinue both chemotherapy and sorafenib. Resume chemotherapy when symptoms have subsided to Grade 1 toxicity or less. Resume with 5-FU and Oxaliplatin at 75% of the previous dose. Resume sorafenib at one dose reduction.

6.3.3.2 Nausea, Vomiting

For Grade 3 to 4 nausea/vomiting that remains uncontrolled despite maximal antiemetic therapy, temporarily discontinue both chemotherapy and sorafenib. Maximal antiemetic therapy includes using such agents as 5-HT3 receptor antagonists, corticosteroids, and benzodiazepines, where indicated. Resume chemotherapy when symptoms have subsided to Grade 1 toxicity or less. Resume with 5-FU and oxaliplatin at 75% of the previous dose. Sorafenib may be resumed at full dose.

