6.4.3 Dose modification for non-hematologic toxicities¹

Recommended dose modification for non-hematologic toxicity (excluding hypertension and hand foot skin reaction, diarrhea and fatigue.									
Grade	Dose Interruption	Dose Modification							
• Grade 0-2	Treat on time	No Change							
• Grade 3	Interrupt until ≤Grade 2	DECREASE one dose level							
• Grade 4	OFF protocol therapy	OFF protocol therapy							
 If no recovery after 21 day delay, treatment will be discontinued unless subject is deriving clinical benefit 									

¹For sorafenib dose reductions for diarrhea, nausea, and vomiting, see sections 6.3.4.1 and 6.3.4.2.

For HFSR, sorafenib and 5-FU should be both reduced; For diarrhea, sorafenib, 5-FU and oxaliplatin should all be reduced; For fatigue, sorafenib, 5-FU and oxaliplatin should all be reduced.

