Doses of sorafenib that have been reduced for any reason will not be re-escalated. For treatment-related non-hematologic toxicities, patients who do not recover to Grade 1 toxicity within 3 weeks will go off Sorafenib for the duration of the study, but they can continue with FOLFOX if they continue to meet treatment criteria for FOLFOX.

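### The sorafenib restart dose after uncontrolled Grade 3-4 nausea or vomiting is ambiguous: section 6.3.3.2 and the 6.4.3 table differ, the footnote linking them cites sections that do not exist, and full dose is undefined for a patient already reduced

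*Combined protocol and SAP*

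**What the plan says.** Section 6.3.3.2 sets the trigger and the hold: "For Grade 3 to 4 nausea/vomiting that remains uncontrolled despite maximal antiemetic therapy, temporarily discontinue both chemotherapy and sorafenib". It restarts 5-FU and oxaliplatin at three quarters of the preceding dose once symptoms have fallen to Grade 1 or below. Of sorafenib it then says: "Sorafenib may be resumed at full dose". The protocol does not define the term full dose. Section 6.4.1 gives a starting dose of 400 mg twice daily and two reduction levels, 400 mg once daily and 200 mg once daily.

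Section 6.4.3 has a general sorafenib table for non-hematologic toxicity, "excluding hypertension and hand foot skin reaction, diarrhea and fatigue". Nausea and vomiting are not on that list. For Grade 3 the table interrupts sorafenib until Grade 2 or lower and then says "DECREASE one dose level". For Grade 4 it says "OFF protocol therapy". Footnote 1 to the section heading refers the reader to sections 6.3.4.1 and 6.3.4.2 for sorafenib reductions for diarrhea, nausea and vomiting.

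The paragraph that closes section 6.4, after the hypertension table, adds: "Doses of sorafenib that have been reduced for any reason will not be re-escalated".

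**The concern.** A treating physician whose patient has just recovered from uncontrolled Grade 3 or 4 vomiting should find one sorafenib instruction. On a literal reading there are two for each grade, one in 6.3.3.2 and one in the 6.4.3 table, and the reference that should settle the matter leads nowhere. For a patient already on a reduced dose there is a further question: whether full dose means the starting dose or the dose held.

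Two things are at stake. One is safety, because one available reading raises the dose of a patient who was reduced for toxicity. The other is interpretation. Tolerability and toxicity are a secondary objective (section 1.2), and in a 40-patient single-arm study the delivered sorafenib dose after the same event would depend on which section the physician followed.

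**Working it through.** The plan has no figure to reproduce here. The check is a comparison of the texts, with a little arithmetic on size.

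**1. The instructions side by side**

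| Place | Events covered | Sorafenib action |
|---|---|---|
| 6.3.3.2 | Grade 3-4 nausea/vomiting, uncontrolled on maximal antiemetics | Hold, then full dose permitted |
| 6.4.3 table, Grade 3 | Non-hematologic toxicity; nausea/vomiting not excluded by the title | Hold, then one level lower |
| 6.4.3 table, Grade 4 | As above | Off protocol therapy |
| End of 6.4 | Any sorafenib dose already reduced | Not raised again |

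Taken literally, the first row differs from the second for Grade 3 and from the third for Grade 4.

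**2. The footnote's targets.** The numbered headings under 6.3 run 6.3.1, 6.3.2, then 6.3.3 with subsections 6.3.3.1 to 6.3.3.5, and the next is 6.4. There is no 6.3.4. The footnote names diarrhea first, then nausea and vomiting. That order matches "6.3.3.1 Diarrhea" and "6.3.3.2 Nausea, Vomiting", so these are probably the sections meant.

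**3. Whether correcting the numbers is enough.** It is not. The footnote promises sorafenib reductions. Section 6.3.3.1 has one for diarrhea (restart one level lower), but 6.3.3.2 has none for nausea or vomiting. Section 6.3.3.2 also covers only uncontrolled events. If the footnote takes all nausea and vomiting out of the table, controlled Grade 3-4 events have no specific sorafenib rule. If it does not, the table and 6.3.3.2 still compete for the uncontrolled ones.

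**4. The ban on re-escalation.** There are two cases.

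- Patient never reduced: sorafenib is held at 800 mg/day (2 × 400 mg) and restarted at 800 mg/day. The ratio is 800/800 = 1, so nothing is re-escalated and nothing conflicts.
- Patient already reduced, with full dose read as the starting dose: from the first reduction level the ratio is 800/400 = 2, and from the second it is 800/200 = 4. Either restart breaks the ban. If full dose means the dose held, the ratio is 1 and there is no conflict.

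**5. How many patients.** The documents give no rate for patients who both have an uncontrolled event and are already reduced. The nearest figures are in section 6.2: Grade 3-4 nausea in 11% and vomiting in 9% on oxaliplatin with 5-FU/LV. If those rates applied here (an assumption), 40 × 0.11 = 4.4 patients would have such nausea and 40 × 0.09 = 3.6 such vomiting. That is between 4.4 patients with either event if the groups overlap fully and 4.4 + 3.6 = 8.0 if they do not overlap. The rates count every Grade 3-4 event, controlled or not, in second-line colorectal cancer without sorafenib. They illustrate scale only, and the affected subset could be anything from none up to those totals.

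**The case against.** The best defence is that the documents show an intention to treat nausea and vomiting separately. Footnote 1 is attached to the heading of 6.4.3 and redirects exactly these events, and the wrong digit is easily guessed. The note under the chemotherapy table in 6.3.3.5 also sets nausea and vomiting apart, as dealt with earlier. Section 6.3.3.2 is the only section specific to these events that gives a sorafenib instruction. Its wording is permissive, so the general bar on raising reduced doses can be read as a limit on it.

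Much of this stands. It rules out two stronger readings that a reader might infer.

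- **That 6.3.3.2 flatly contradicts the re-escalation rule.** It does not. The section holds sorafenib and does not reduce it, while the rule concerns doses already reduced. Conflict needs both an earlier reduction and full dose read as the starting dose.
- **That one event carries three incompatible instructions.** It does not. Never raising a reduced dose is compatible with going down a level and with stopping. At most two instructions compete for any one grade, and the footnote was apparently meant to choose between them.

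The defence does not dispose of the point. The 6.3.3.5 note is written for 5-FU and oxaliplatin, and it names nausea and vomiting among its exclusions where the 6.4.3 title does not. Correcting the footnote's digits leads to a section without the reduction it promises. Full dose also remains open: in the same paragraph chemotherapy restarts relative to the previous dose, while sorafenib is given a different, undefined term.

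**Conclusion.** The point holds as an unclear carve-out with a broken cross-reference and an undefined term. The footnote error is certain. The difference between 6.3.3.2 and the 6.4.3 table is present on a literal reading, although separate handling was probably intended. The conflict with the re-escalation rule is conditional. It reaches only a patient already reduced, and only if full dose means 400 mg twice daily; the restart would then be 2 or 4 times the current daily dose.

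A reader might take the section 6.2 rates to mean that about 4 of the 40 patients face that risk. The documents do not support this, because those rates are neither limited to uncontrolled events nor to patients already reduced, and they come from another population and regimen.

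Sample size, power and alpha are unaffected. The matter should be corrected because it bears on safety and on how the tolerability data are read.

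**What to change.** Reconcile section 6.3.3.2, the title and footnote 1 of section 6.4.3, and the re-escalation sentence at the end of section 6.4. The revised text should:

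- give one sorafenib instruction for Grade 3 and one for Grade 4 nausea/vomiting, and make clear whether events controlled by antiemetics are covered;
- state whether the 6.4.3 table applies to nausea and vomiting;
- correct the section numbers in footnote 1 and make its description match what the cited sections contain;
- state what full dose means for a patient whose sorafenib has already been reduced.

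The clinical team decides which rule stands; this review takes no position on it. The cost is a wording amendment to these places, with no added patients, visits or procedures.

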6.3.3.3 Melena and Hematemesis

If melena or hematemesis occur during therapy, sorafenib and chemotherapy should be held for Grade 1 toxicities until they resolve. For patients who develop Grade 3 or 4 toxicities, therapy should be discontinued and the Principal Investigator notified.

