3.2 Exclusion Criteria

- The patient has either clinically apparent central nervous system metastases or carcinomatous meningitis
- The patient is a woman who is pregnant or lactating. Women of childbearing potential must have a negative serum pregnancy test performed within 7 days prior to the start of study drug. Post-menopausal women (defined as no menses for at least 1 year) and surgically sterilized women are not required to undergo a pregnancy test. All patients (men and women) of childbearing potential must agree to use adequate contraception beginning at the signing of the ICF until at least 30 days after the last dose of study drug. The definition of adequate contraception will be based on the judgment of the principal investigator or a designated associate.
- Active or clinically significant cardiac disease including:
 - Congestive heart failure New York Heart Association (NYHA) > Class II.
 - Active coronary artery disease.
 - Cardiac arrhythmias requiring anti-arrhythmic therapy other than beta blockers or digoxin.
 - QTc > 500 ms
 - Unstable angina (anginal symptoms at rest), new-onset angina within 3 months before randomization, or myocardial infarction within 6 months before randomization.
- Evidence or history of bleeding diathesis or coagulopathy.
- Subject with any pulmonary hemorrhage/bleeding event of NCI-CTCAE v4.0 Grade 2 or higher within 4 weeks before enrollment; any other hemorrhage/bleeding event of NCI-CTCAE v4.0 Grade 3 or higher within 4 weeks before enrollment.
- Presence of a non-healing wound, non-healing ulcer, or bone fracture.
- History of organ allograft. (including corneal transplant).
- Any malabsorption condition.

- Uncontrolled hypertension defined as systolic blood pressure > 150 mmHg or diastolic pressure > 90 mmHg, despite optimal medical management.
- Uncontrolled ascites defined as not easily controlled by stable doses of diuretics.
- Known human immunodeficiency virus (HIV) infection.
- The patient has a medical or psychiatric condition that constitutes an unacceptable risk for participation in this trial, in the judgment of the treating physician.
- The patient has received any investigational agents within 4 weeks prior to their first dose of sorafenib.
- ECOG status of ≥ 2
- Child-Pugh B or C cirrhosis (CTP score \geq 7) (See Appendix A)
- CLIP score >3 (See Appendix A) Inability to comply with study and/or follow-up procedures

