6.3 Dose Modification of 5-FU and Oxaliplatin

6.3.1 Toxicity will be evaluated weekly during the sorafenib lead-in period, weekly during the first 3 weeks of cycle 1 of FOLFOX-Sorafenib, and then once every two weeks for subsequent cycles. Dose modifications based on significant weight changes can be made in accordance to institutional practice.

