6.3.3.5 Dose Modifications for Other Non-Hematologic Toxicity

CTC Grade	Action	5-FU, % of	Oxaliplatin, % of		
		Previous Dose	Previous Dose		
1	Continue therapy	100	100		
2	Continue therapy	100	100		
3	Resume when	75 ^{1, 3}	75 ^{2, 3}		
	toxicity <= Grade 1				
4	Resume when	50 ^{1, 3}	50 ^{2, 3}		
	toxicity <= Grade 1				

¹See section 6.4.4 for dose reductions of 5-FU for Hand-Foot-Skin Reaction.
 ²No Dose reduction of Oxaliplatin for Grade 3 or 4 Hand-Foot-Skin Reaction.
 ³No dose reduction of 5-FU or Oxaliplatin need to be made for asymptomatic Grade 3 or 4 Amylase or Lipase elevation.

Pertains to treatment-related toxicity, not including diarrhea, nausea/vomiting, melena/hematemesis, neurologic toxicity (see above). Sorafenib dose should be adjusted as per the table in Section 6.4.1. For hematologic toxicity, see Section 6.3.2.

Doses of chemotherapy that have been reduced will not be re-escalated. Patients who do not recover to Grade 1 within 6 weeks will go off study.

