6.4 Dose Modification for Sorafenib

Expected adverse events from sorafenib: diarrhea (43%), increased lipase (41%), increased amylase (30%), nausea (23%), anorexia (16%), vomiting (16%), and constipation (15%), rash/desquamation (40%), hand-foot skin reaction (30%), alopecia (27%), pruritus (19%), and dry skin (11%), hyperthyroidism, hypertension (17%), angioedema, and congestive heart failure, hypoalbuminemia (49%), hemorrhage (15%) (i.e., gastrointestinal, respiratory tract and rarely cerebral hemorrhage), dyspnea (14%) and cough (13%), hypocalcemia (20%), and hypophosphatemia (40%).

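### Section 6 has no hold rule for Grade 2 melena or hematemesis, and the only immediate written sorafenib instruction at that grade is to continue unchanged; secondarily, the three-week sorafenib limit is stated with and without a clinical-benefit exception

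*Combined protocol and SAP*

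**What the plan says.** **Bleeding.** Section 6.3.3.3 is the specific rule for melena and hematemesis. At the lowest grade "sorafenib and chemotherapy should be held for Grade 1 toxicities until they resolve". At the top, "For patients who develop Grade 3 or 4 toxicities, therapy should be discontinued and the Principal Investigator notified". It does not mention Grade 2.

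Two general tables surround it. The 5-FU and oxaliplatin table in Section 6.3.3.5 covers other treatment-related toxicity, "not including diarrhea, nausea/vomiting, melena/hematemesis, neurologic toxicity (see above". The sorafenib table in Section 6.4.3 is headed "Recommended dose modification for non-hematologic toxicity (excluding hypertension and hand foot skin reaction, diarrhea and fatigue"; bleeding is not among those exclusions. Its footnote sends diarrhea, nausea and vomiting elsewhere (to 6.3.4.1 and 6.3.4.2, although the relevant text is numbered 6.3.3.1 and 6.3.3.2) and does not mention bleeding. For Grades 0 to 2 the table continues sorafenib on schedule with no dose change.

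**Sorafenib after Grade 3 non-hematologic toxicity.** Section 6.4.3 interrupts until Grade 2 or less, then resumes one dose level down. After 21 days without recovery it discontinues, except in a patient who is benefiting. Footnote a of Section 6.4.5 has a similar exception for hypertension. The closing paragraph of Section 6.4, printed after the hypertension table but worded for treatment-related non-hematologic toxicity generally, takes the patient off sorafenib for the rest of the study unless toxicity is back to Grade 1 within three weeks. Section 6.0 caps any sorafenib interruption at three weeks, whatever the cause. Neither of these last two mentions an exception.

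**The concern.** The protocol treats Grade 1 gastrointestinal bleeding as serious enough to stop both treatments. At the next grade up it gives no FOLFOX instruction and, for sorafenib, only a general row that continues treatment. That reverses the expected order of caution.

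The patients may have Child-Pugh A cirrhosis, and sorafenib inhibits the VEGF receptors. Section 6.4 lists "hemorrhage (15%) (i.e., gastrointestinal, respiratory tract and rarely cerebral hemorrhage" among its expected adverse events. At entry, non-pulmonary bleeding is excluded by grade only for "any other hemorrhage/bleeding event of NCI-CTCAE v4.0 Grade 3 or higher within 4 weeks before enrollment", so a recent Grade 2 gastrointestinal bleed does not in itself bar enrollment.

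The secondary matter affects consistency of dosing. For a small set of patients, the paragraph followed decides whether sorafenib continues or ends. Tolerability is a secondary objective, so the two outcomes should not depend on that choice.

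**Working it through.** No plan figure has to be reproduced. The check sets the rules side by side.

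**Step 1: melena or hematemesis, by grade.**

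| Grade | 6.3.3.3 (both treatments) | 6.3.3.5 (FOLFOX) | 6.4.3 (sorafenib, as worded) |
|---|---|---|---|
| 1 | Hold until resolved | Excluded | Continue, dose unchanged |
| 2 | Silent | Excluded | Continue, dose unchanged |
| 3 | Discontinue | Excluded | Interrupt, then one level down |
| 4 | Discontinue | Excluded | Off protocol therapy |

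If the specific section governs wherever it speaks, Grades 1, 3 and 4 are settled. At Grade 2 it does not speak. FOLFOX then has no rule. Sorafenib has either the 6.4.3 row or, if 6.4.3 is thought not to reach bleeding at all, no rule. Neither reading produces a hold.

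**Step 2: does another rule catch Grade 2?** The closing paragraph of 6.4 does, but late: it ends sorafenib if treatment-related toxicity is not at Grade 1 within three weeks (21 days). It is not an immediate hold and says nothing about stopping FOLFOX.

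**Step 3: sorafenib after Grade 3 toxicity.** "The starting dose of sorafenib is 400 mg twice a day", which is 2 × 400 = 800 mg/day. The first reduction level is 400 mg once daily. Three illustrative patients who start at full dose:

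- *Grade 2 on day 10, Grade 1 by day 21.* Section 6.4.3 resumes at 400 mg/day on day 10, and the closing paragraph's limit is met. No conflict.
- *Grade 2 on day 10, still Grade 2 on day 21.* Section 6.4.3 gives 400 mg/day; the closing paragraph gives 0 mg/day for the rest of the study. The hold lasted 10 days, so the cap in 6.0 is not breached.
- *Still Grade 3 on day 21, with clinical benefit.* Section 6.4.3 does not require discontinuation. The closing paragraph does, and a longer hold exceeds the cap in 6.0. The hypertension exception in 6.4.5 meets the same cap.

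**Step 4: how many patients?** The only relevant rate is 15% hemorrhage, all sites, with no split by grade: 40 × 0.15 = 6 patients. That is context only. The number with Grade 2 gastrointestinal bleeding, or in the second or third situation of Step 3, cannot be derived from the documents.

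**The case against.** **Clinicians would hold anyway.** Many would extend the Grade 1 hold to Grade 2, and Section 6.5 allows treatment to stop for unacceptable adverse events or on the investigator's judgment. There are partial safeguards. Grade 3 hemoglobin reduces sorafenib (6.4.1), Grade 3 or higher anemia holds FOLFOX (6.3.2), and Section 3.2 excludes bleeding diathesis, coagulopathy and findings that put a patient at high risk of treatment complications. All of this stands and lowers the practical risk. None of it is a written hold for a Grade 2 bleed.

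**The bleeding sections do not conflict throughout.** A reader might infer from the table that they disagree at Grades 1 and 3 as well. The documents do not force that reading: 6.3.3.3 is specific, names sorafenib, and is the section to which 6.3.3.5 points back. Only Grade 2 is left open.

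**Resuming and stopping are different things.** Section 6.4.3 sets when to resume; the closing paragraph of 6.4 and Section 6.0 set outer limits. A patient can satisfy all of them, as the first case in Step 3 shows. This stands and narrows the secondary point. It does not reconcile toxicity stuck at Grade 2 or worse at three weeks, or use of the benefit exception. Nor does the different restart grade for hand-foot skin reaction add to the conflict, since 6.4.3 expressly excludes that reaction.

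**Conclusion.** The main point holds: one grade is missing from the gastrointestinal bleeding rule, and the only immediate written sorafenib instruction at that grade is to carry on. This is a patient-safety wording fault that should be fixed. It rests on reading the scope statements of 6.3.3.5 and 6.4.3 as written.

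Two stronger readings are not supported. A reader might infer that the protocol orders full-dose sorafenib during a Grade 2 bleed. The row says no change, which means 800 mg/day only for a patient not already reduced, and the three-week stop still applies to treatment-related bleeding. A reader might also size the gap by counting doses up to the next scheduled toxicity review. That would count ordinary dosing and assume no unscheduled contact after a known bleed; it does not measure the gap.

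The secondary point holds only for toxicity still at Grade 2 or worse at three weeks, or where a benefit exception is invoked. No discontinuation-rate endpoint is defined, so its consequence is for consistency of treatment and of the tolerability record. Neither point affects the sample size, and no effect on the time-to-progression analysis is claimed.

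**What to change.** **Bleeding.** In 6.3.3.3, replace Grade 1 with Grade 1-2, so that sorafenib and FOLFOX are both held until the bleed resolves. Add melena and hematemesis to the exclusions in the 6.4.3 table heading, and to its footnote with a reference to 6.3.3.3. Correct the footnote's other section numbers at the same time.

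**Sorafenib at three weeks.** State one three-week rule, and say in 6.0, 6.4.3, 6.4.5 and the closing paragraph of 6.4 whether the clinical-benefit exception applies. Keeping or deleting it is a clinical trade-off, because sorafenib is the standard treatment in this setting. That choice belongs to the investigator; the sections need only agree.

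**Cost.** A short amendment to the wording of Section 6, with the IRB approval that Section 13.1 requires. No new data, visits or procedures.
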